The study population for this project will include neonates and infants (less than 1-year-old) who are undergoing repair of aortic coarctation via thoracotomy with no other simultaneous surgical procedure. The patients will undergo a standardized anesthetic. Patients in the experimental arm will receive a paravertebral nerve block for intraoperative and postoperative pain control supplemented with narcotic as needed while the control arm will receive standard of care, which will include additional narcotic as indicated and local anesthetic infiltrated into the wound after the procedure. Each group will have their spinal cord regional saturations measured with NIRS. Regional anesthetic techniques in children are relatively low risk endeavors and the primary concern is risk of regional block failure. More significant, but very rare complications could include local anesthetic systemic toxicity (LAST), tissue hematoma (bleeding), epidural hematoma (bleeding), unintentional epidural spread, and prolonged sensory blockade. [5]

The primary aim of this study is to determine the feasibility of studying whether a single-shot paravertebral nerve block is effective in providing intraoperative and postoperative pain control in infants undergoing a thoracotomy for coarctation of the aorta. This will be determined by comparing morphine equivalent consumption in the standard of care and intervention groups. Secondary outcomes include plasma epinephrine levels (three times per patient) to determine stress hormone response in both groups, NIRS values to monitor the difference in spinal cord oxygen supply between the intervention and control group, time to first feeding (another measure of pain control in this age group), and total ventilator time.

The following aims are proposed:

Primary Aim

1. Determine the feasibility of studying whether total narcotic administration is less in subjects who receive the peripheral nerve block versus standard of care.

Hypothesis: Patients undergoing the experimental technique, paravertebral nerve block, will have less pain and therefore will consume fewer morphine equivalents in the 48-hour post-op follow-up period. This difference will be measurable and provide sample size estimations for future studies.

Evaluation Method: All narcotics used in the 48-hour post-op period will be tabulated and converted to morphine equivalents. Other non-narcotic analgesics will also be tabulated, but can't be converted to morphine equivalents.

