Secondary Aims

2. Measure whether spinal cord perfusion can be improved during aortic cross clamp by improving collateral blood flow with regional anesthesia techniques.

Hypothesis: Near infrared spectroscopy (NIRS) values will decrease in the control and study group during aortic cross clamp but values in the study group will be 41% higher than control due to increased collateral blood flow.

Evaluation Method: Continuous measurement of spinal cord NIRS values during repair of aortic coarctation, including the aortic cross clamp period.

3. Determine the total time required for post-op ventilation in each group.

Hypothesis: Post-op ventilation times will be lower in those patients undergoing the experimental technique, paravertebral nerve block, because these patients will have less respiratory splinting from better analgesia and be less sedated from less sedative and analgesic use.

Evaluation Method: Time until extubation.

4. Determine the time to first feeding in each group.

Hypothesis: Patients who undergo the experimental technique, paravertebral nerve block, will have earlier return to feeding since they will have better analgesia and less sedation from narcotics.

Evaluation Method: Time until first feeding.

5. Measure stress response to surgery in the experimental and control groups.

Hypothesis: Patients who undergo the experimental technique, paravertebral nerve block, will have better suppression of the natural stress response to surgery.

Evaluation Method: Plasma epinephrine levels measured at baseline (before incision), postoperatively (just before transfer to the Intensive Care Unit), and 24 hours postoperatively.

Introduction, Background, and Significance to Our Mission

Repair of aortic coarctation is a commonly performed operation. The repair is performed via thoracotomy which is a surgical incision that is commonly complicated by atelectasis, desaturation, and pain in the adult population. To prevent these complications, it has been shown that regional or neuraxial anesthesia can decrease the amount of pain the patient has, which allows for deeper breathing and fewer desaturations from atelectasis. We propose, in this study, to examine the benefits of paravertebral peripheral nerve block in the neonatal and infant populations. Regional anesthesia has the potential to decrease narcotic requirements in children undergoing painful operations, decrease ventilator time, and manipulate the stress response to surgery. [1] [2] [3]

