Participants in the control arm will undergo an anesthetic consistent with the standard of care. The patient will be induced for anesthesia with propofol 3mg/kg or ketamine 2mg/kg (if there is intravenous access) or sevoflurane with 1 mcg/kg of fentanyl and 1.2 mg/kg rocuronium once IV access is established. The patient will be intubated; intravenous and intra-arterial access will be obtained and the patient will be positioned for surgery. A NIRS pad will be used for cerebral oximetry as well as another NIRS pad for spinal cord oximetry. Fentanyl may be used as needed for additional analgesia and anesthesia will be maintained with sevoflurane. The skin will be infiltrated at the conclusion of surgery with less than 1 mL/kg of 0.25% bupivacaine with epinephrine 1:200k. The patient will be returned to the ICU intubated unless the anesthesia provider considers them to be an excellent candidate for early extubation. Every patient will have an epinephrine level drawn pre-incision in the operating room, post-operatively upon arrival to the intensive care unit, and 24-hours post-operatively (unless there is no existing vascular access that allows the level to be drawn 24-hours post-operatively). The 24-hour post-operative time point will be defined as 24-hours after arrival to the CICU.

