Participants in the experimental arm will undergo an anesthetic that includes the regional anesthetic technique, paravertebral nerve block. The patient will be induced for anesthesia with propofol 3mg/kg or ketamine 2mg/kg (if there is intravenous access) or sevoflurane with 1 mcg/kg of fentanyl and 1.2 mg/kg rocuronium once IV access is established. A NIRS pad will be used for cerebral oximetry as well as another NIRS pad for spinal cord oximetry. The patient will be intubated, and then will be positioned laterally for the nerve block at approximately the left T3-4 level. A 13-6 MHz, linear ultrasound probe with a sterile sheath will be used to provide imaging for the paravertebral nerve block. A Pajunk SonoPlex 50mm, 22 gauge, facet tip needle will be used. The injected solution will be 1 mL/kg of 0.2% ropivacaine with 5 mcg/mL (1:200k) epinephrine. Ropivacaine is a standard drug used in this patient population for regional nerve blocks and is non-experimental as part of this protocol. The paravertebral block needle insertion site and sterile field will be observed and the block will be performed or supervised by one of the study investigators. Fentanyl may be used as needed for additional analgesia and anesthesia will be maintained with sevoflurane. The skin will not be infiltrated with additional local anesthetic at the conclusion of the case. Every patient will have an epinephrine level drawn pre-incision in the operating room, post-operatively upon arrival to the intensive care unit, and 24-hours post-operatively (unless there is no existing vascular access that allows the level to be drawn 24-hours post-operatively). The 24-hour post-operative time point will be defined as 24-hours after arrival to the CICU.

Post-operative pain control in either the control or experimental (paravertebral nerve block) group will be accomplished with intravenous, rectal, and oral analgesics. Patients will receive scheduled rectal acetaminophen while intubated and oral acetaminophen once they have progressed to oral intake of formula. Intravenous fentanyl or morphine will be used for

breakthrough pain while intubated and until oral intake is tolerated. Once oral intake is resumed, the patient will be provided with oral oxycodone as needed for pain and additional doses of IV morphine as needed for severe pain.. If the patient is not yet ready for extubation and requires additional sedation, intravenous doses of midazolam may be required.

Sample Size/Statistics

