Descriptive statistics will be calculated for all variables of interest and include means and standard deviations, medians and ranges or counts and percentages, as appropriate. Summary measures will be tabulated overall and by treatment group. Recruitment and consent rates will be calculated with associated 95% confidence intervals. Primary and secondary outcomes will be compared between the two intervention groups. Continuous measures will be compared between groups using two-sample t-tests or Wilcoxon rank-sum tests while categorical variables will be compared using Chi-square tests or Fisher exact tests. Because this is a pilot study, effect sizes will be calculated for all outcomes and will include difference in means, difference in rates, or risk ratios with associated 95% confidence intervals. Analysis will follow the intention to treat principal where all subjects are analyzed based on their randomly assigned treatment whether or not they received the treatment. A p-value less than 0.05 will be considered statistically significant and all statistical testing will be two-sided, unless otherwise noted. Analysis will be conducted using SAS v. 9.4 (Cary, NC) and under direction of the pediatric biostatistics core.

Adverse Event Reporting

Monitoring of Adverse Events (AEs) and Serious Adverse Events (SAEs) is an important aspect of data collection. The study subjects will be reviewed on a case-by-case basis. The principal investigator will determine the seriousness of each adverse event and whether or not the event

was related to the study. Adverse events potentially associated with paravertebral nerve blocks include (from most to least common): block failure, vascular puncture, deep tissue hematoma (SAE), epidural hematoma (SAE), hypotension, lung puncture, pneumothorax, and local anesthetic systemic toxicity (SAE). Hypotension will be defined as a mean arterial pressure less than 30 mm Hg during the first 24 hours after arrival to the CICU.

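### The 24-hour epinephrine comparison is limited to infants who still have vascular access, a post-randomisation condition that the block could influence, and the plan has no analysis for the missing values

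*Combined protocol and SAP*

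**What the plan says.** The abstract names the outcome: "Secondary outcomes include plasma epinephrine levels (three times per patient) to determine stress hormone response in both groups". Aim 5 under Secondary Aims lists the three times: "Plasma epinephrine levels measured at baseline (before incision), postoperatively (just before transfer to the Intensive Care Unit), and 24 hours postoperatively". Study Description repeats the schedule for each arm and attaches an exception to the last sample only, in the same words for control and block: it is drawn "unless there is no existing vascular access that allows the level to be drawn 24-hours post-operatively". It also fixes the clock: "The 24-hour post-operative time point will be defined as 24-hours after arrival to the CICU".

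Sample Size/Statistics treats all continuous outcomes alike: "Continuous measures will be compared between groups using two-sample t-tests or Wilcoxon rank-sum tests". It adds that "effect sizes will be calculated for all outcomes", with 95% confidence intervals, and that analysis follows randomised assignment. It gives no rule for missing outcome values, no repeated-measures model, no sensitivity analysis, and no plan to report missing samples by arm.

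Under Secondary Aims, Aims 3 and 4 expect shorter ventilation and earlier feeding with the block.

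**The concern.** The protocol builds missing values into a named secondary outcome and then applies a test that silently drops them. Whether an infant still has access 24 hours after reaching the CICU is known only after randomisation. If access tends to be lost sooner in infants who recover faster, and the block speeds recovery as Aims 3 and 4 suppose, the infants left in the comparison are selected differently in the two arms. More of the low-epinephrine infants would then be missing from the block arm, and the difference would look smaller than it is.

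Sample Size/Statistics says that the effect sizes will feed the design of a larger trial. A wide confidence interval would tell its planners about imprecision but not about selection.

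**Working it through.** The documents give no epinephrine effect, SD, missing fraction or power, so there is no planned figure to reproduce. From the documents come 15 infants per arm, the two-sample test and the two-sided 0.05 level. Everything else below is assumed.

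**1. Size of the possible shrinkage.** Let S be a recovery score (higher means slower), with mean 0 in control and -0.5 in block, and SD 1. Let 24-hour log epinephrine be 0.7 × S plus noise, with SD 1 within each arm. The true difference is 0.7 × (-0.5) = -0.35 SD. Let access be lost when an index L, with correlation r to S, falls below c, the control 20th percentile: c = -0.842. In block the standardised cut-off is c + 0.5r. With λ(x) = φ(x) / (1 - Φ(x)), the expected complete-case difference is

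-0.35 + 0.7 × r × [λ(c + 0.5r) - λ(c)], where λ(c) = 0.350.

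| r | Block missing, Φ(c + 0.5r) | λ(c + 0.5r) | Shift (SD) | Estimate (SD) |
|---|---|---|---|---|
| 0.3 | 24% | 0.416 | 0.014 | -0.34 |
| 0.5 | 28% | 0.463 | 0.040 | -0.31 |
| 0.7 | 31% | 0.513 | 0.080 | -0.27 |
| 1.0 | 37% | 0.594 | 0.171 | -0.18 |

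At r = 1.0 with 30% missing in control, the estimate is -0.15 SD. The last row is the extreme case, in which recovery alone decides who loses access.

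**2. Direction.** A second calculation sets the missing rate in each arm separately and lets loss of access correlate (rho) with the infant's own epinephrine level. It assumes a true effect of 1.06 SD, which gives 80% power for a t-test at 15 v 15 (4,000 simulated trials per row; results at rho 0.3, 0.5, 0.7).

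| Missing, control / block | Estimate (SD) | Power |
|---|---|---|
| 20% / 20% | 1.06, 1.05, 1.05 | 71%, 73%, 79% |
| 40% / 40% | 1.06, 1.06, 1.05 | 57%, 62%, 68% |
| 20% / 40% | 0.97, 0.91, 0.85 | 56%, 54%, 55% |
| 20% / 60% | 0.88, 0.75, 0.62 | 39%, 31%, 26% |
| 40% / 20% | 1.13, 1.20, 1.26 | 69%, 78%, 87% |

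Equal missing rates mainly cost power. More missing in block shrinks the difference. More missing in control exaggerates it.

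**3. Setting against sampling error.** With complete data at 15 v 15, the 95% interval has a half-width of 2.048 × √(2/15) = 0.75 SD, and power for a true 0.35 SD is about 15%. The largest shift in step 1 is 0.17 SD.

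**4. What a model recovers.** In the step 1 setting, a large-sample simulation of an arm-by-time model that also used the post-operative sample moved -0.18 to between -0.19 and -0.25, and -0.27 to between -0.28 and -0.31. The gain depends on how closely that sample tracks recovery. It remained when the control mean at the post-operative sample was shifted.

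**The case against.** The strongest reply is that the mechanism is inferred. A reader might conclude that the test compares only slow-recovering infants, or that the block's best responders drop out. The documents do not support that. They do not say when or why lines are removed, they do not tie access to recovery, and Aims 3 and 4 concern ventilation and feeding. Study Description also foresees intravenous morphine for severe pain after oral intake resumes, so a recovering infant may still have access. This stands: the bias is possible, and its direction is unknown.

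A reader might also take the loss of about half the effect as the expected size. It requires r = 1.0; at 0.3 to 0.7 the loss is 0.01 to 0.08 SD. Nor is the intention-to-treat statement breached, since it concerns analysis by assigned arm and is silent on absent laboratory values.

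The reply is also right about scope. This is one of three time points of a secondary outcome, in a pilot that describes itself as probably underpowered and whose primary goal is feasibility. The other two samples and the morphine outcome are untouched.

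What remains is that the plan foresees missing values on a post-randomisation condition and has no method for them. Low power does not answer that.

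**Conclusion.** The point holds as a minor one. As planned, the 24-hour comparison is a complete-case analysis conditioned on access, which the block could influence under the protocol's own hypotheses. It may preferentially exclude faster-recovering infants and shrink the Aim 5 difference. Under the assumptions in step 1, a true -0.35 SD is seen as -0.34 to -0.27 SD for correlations of 0.3 to 0.7, and as -0.18 SD only at the extreme. With other missing patterns the result would be lost power alone, or exaggeration. The documents cannot settle which applies, so the plan should let the data show it.

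**What to change.** In Sample Size/Statistics:

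1. Analyse log epinephrine in a likelihood-based repeated-measures model with arm-by-time terms and unstructured covariance, so that infants without a 24-hour value still contribute. Do not use the pre-incision value as a baseline covariate unless it is drawn before the block. The documents place it before incision but do not say whether it precedes the block, and the block solution contains epinephrine.
2. Add a rank-based sensitivity analysis that places infants whose line was removed because of recovery at the favourable end, and show the opposite placement beside it.
3. Report 24-hour sample availability and the reason for absence by arm, and state that the 24-hour result does not cover all randomised infants.

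Making the post-operative sample the main comparison instead would not be sound. Study Description has control infants, but not block infants, receive wound infiltration containing epinephrine at the end of surgery, shortly before that sample. Its timing is also inconsistent: Aim 5 puts it before transfer to the ICU, and Study Description puts it on arrival there. These passages must be reconciled.

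The cost is a few sentences and a little more analysis, with no extra blood draw. The model only partly removes the bias if missingness depends on unmeasured recovery, which is why the sensitivity analysis is needed.

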This protocol is designed as a pilot study with limited-efficacy testing. The primary goal is to demonstrate the feasibility of a subsequent randomized clinical trial. In doing so, we will assess the capacity for recruitment and caregiver consent to random assignment. An additional exploratory aim is to evaluate the preliminary efficacy of using a single-shot paravertebral nerve block to decrease perioperative morphine consumption. Because this is a pilot study, the proposed study is likely underpowered to detect a statistically significant result. However, the results (i.e. effect sizes) from this study will be used in sample size and power calculations for a future, larger RCT. We expect that there will be a trend toward lower morphine equivalent consumption in the experimental group that will either reach statistical significance or provide a better estimation of necessary sample size for future funding from extramural sources.

The most similar study available for comparison examined the use of paravertebral nerve catheters in infants undergoing thoracotomy to repair long-gap esophageal atresia. This study was retrospective and several days of morphine consumption were observed. In this retrospective trial of 17 patients, the authors observed a decrease of 36% in morphine consumption per day ($p<0.001$).[6] If such a dramatic decrease in morphine consumption is observed during our prospective study, then it is adequately powered at current sample size 15 in each arm, total 30 patients.

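### The effect observed with 15 infants per arm is named as the sizing input for the next RCT; that RCT should be sized on a difference fixed in advance, with the pilot supplying the SD and the recruitment and consent rates

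*Combined protocol and SAP*

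**What the plan says.** Three statements make sizing the next trial a written purpose of this pilot.

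- Sample Size/Statistics: "the results (i.e. effect sizes) from this study will be used in sample size and power calculations for a future, larger RCT". The bracketed gloss identifies the effect size as the input.
- Primary Aim, hypothesis on morphine equivalents: "This difference will be measurable and provide sample size estimations for future studies".
- Sample Size/Statistics, on the expected trend: it will reach significance or "provide a better estimation of necessary sample size for future funding from extramural sources".

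The same section acknowledges imprecision ("the proposed study is likely underpowered to detect a statistically significant result"). It plans effect sizes as "difference in means, difference in rates, or risk ratios with associated 95% confidence intervals", and descriptive statistics that include standard deviations by treatment group. It also states: "Recruitment and consent rates will be calculated with associated 95% confidence intervals".

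The documents give no target or clinically important difference in morphine equivalents for the future RCT and no assumed SD. They do not say how the interval would enter the sizing. The 36% decrease is an external, retrospective catheter result, used only to say when this pilot would be adequately powered. The 41% in Secondary Aim 2 concerns NIRS.

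**The concern.** An effect estimated from 30 infants is a poor basis for sizing a trial. If the pilot happens to overestimate the effect, the next trial is planned too small. If it underestimates the effect, the next trial looks unaffordable or is never run. Reporting a confidence interval does not solve this, because at 15 per arm the interval usually spans everything from a small trial to no finite sample size.

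A difference that matters clinically does not depend on the pilot's sampling error. It is most credible when fixed before the pilot results are seen, which makes this protocol a natural place to commit to it. What is at stake is the power of the next trial, not the validity of this one.

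**Working it through.** **Inputs from the documents.** 15 per arm, 1:1 allocation, two-sided 0.05, 95% confidence intervals with effect sizes, and a future RCT described as larger than the pilot.

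**Assumed, because not given.** Normal outcome with equal SDs, all 30 infants evaluable, 80% target power, and true standardised effect d = 0.2, 0.36, 0.5, 0.72 or 1.03. Three of these are the 36% decrease at an assumed coefficient of variation: 0.36/1.00 = 0.36, 0.36/0.50 = 0.72, 0.36/0.35 = 1.03.

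**The plan's own figure.** For a 36% decrease the plan says of the pilot: "then it is adequately powered at current sample size 15 in each arm, total 30 patients". It gives neither a power nor an SD, so this cannot be reproduced. At 80% power, 15 per arm needs d = (1.96 + 0.8416) × √(2/15) = 1.02. A 36% decrease reaches that only if the coefficient of variation is at most 0.36/1.02 = 0.35.

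**Width of the interval.** Half-width for d = t(0.975, 28 df) × √(2/15) = 2.048 × 0.365 = 0.748 SD. With 12 evaluable per arm it is 0.85.

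**What the interval implies for N.** N per arm = 2 × (1.96 + 0.8416)² / d² = 15.70/d², rounded up. An observed d of 0.5 has interval −0.25 to 1.25: 63 per arm at the estimate, 11 at the upper limit (fewer than the pilot's own 15) and no finite N at the lower limit. The lower limit is above zero in only 8%, 16%, 26%, 48% and 78% of pilots at the five true effects.

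**Sizing on the point estimate (illustration).** Simulate pilots, set N = 15.70/d_obs² rounded up for any favourable result, and raise N to 16 where it is smaller, since the next RCT is to be larger. True power is Φ(d√(N/2) − 1.96). It is below 50% when N < 2 × (1.96/d)².

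| True d | Power is below 50% when N per arm is under | Share of all pilots, N at least 16 |
|---|---|---|
| 0.2 | 192.1 | 41% |
| 0.36 | 59.3 | 34% |
| 0.5 | 30.7 | 28% |
| 0.72 | 14.8 | 0% |
| 1.03 | 7.2 | 0% |

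The two zeros follow directly: N of 16 already exceeds the threshold. At d = 0.5, where 63 per arm are needed, 91% of pilots are favourable. Among those, the 10th to 90th percentile of planned N is 16 to about 600 per arm.

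**Sizing on a fixed difference with the pilot SD.** N = 15.70 × s² × f / d², where d is the chosen difference in true-SD units, s² is distributed as χ²(28)/28, and f is the allowance. These figures are without the 16-per-arm minimum, which could only lower the shares below.

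- True effect equal to the chosen difference, f = 1: power below 50% in about 1% of trials and below 80% in 45–53%.
- Upper one-sided 80% limit for the SD: f = 28/χ²(0.20, 28) = 28/21.59 = 1.297, that is SD × 1.14. Power is below 50% in about 0.1% and below 80% in 15–20%. At d = 0.5 the 10th to 90th percentile of N is 56 to 111 per arm.
- Same allowance, true effect 75% of the chosen difference: below 50% in up to about 9%.
- Same allowance, true effect half of the chosen difference: below 50% in about 95%.

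**Skewed outcome.** The plan allows "two-sample t-tests or Wilcoxon rank-sum tests", so skewness is foreseeable. With a lognormal outcome (assumed coefficient of variation 0.5–1.0, reduction 20–36%), the SD on the raw scale and the same allowance, up to about 16% of trials fall below 50% power and 36–55% below 80%.

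**The case against.** The strongest case against is that nothing wrong has been done yet. The plan names an input for a later calculation and warns that the pilot is likely underpowered. It attaches intervals to every effect, and the next RCT will have its own protocol. Much of this stands, and it limits the point in four ways.

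- A reader might infer that the point estimate alone will size the RCT. The plan does not say so. The percentages for that rule are illustrations, and they also suppose that a trial follows any favourable result, however small.
- A reader might infer that the risk holds across all plausible effects. Without a minimum size, the simulation gives 20% and 14% below 50% power at d = 0.72 and 1.03. Every one of those trials has at most 14 or 7 per arm, which is not larger than the pilot, so the documents do not support those figures.
- A reader might infer that the pilot will provide no SD. It will: SDs by arm are already planned. Only an assumed value is absent.
- A fixed difference protects power at that difference, not below it. Judged by the same below-50% measure, it does badly if the true effect is half as large, although low power for effects smaller than the important one is usually accepted.

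What remains is that the text names the observed effect as the input, and admitting imprecision does not say how it will be handled. Leaving the choice to the next protocol means that the difference is chosen with the pilot result in view.

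**Conclusion.** The concern holds as a minor point about a stated secondary use of the pilot. The plan names the effect observed with 15 per arm as the sizing input, its 95% interval is about ±0.75 SD, and no target difference is given. If the point estimate were used and the next RCT had at least 16 per arm, true power would fall below 50% in roughly 28–41% of pilots at true effects of 0.5 SD or less, and in none at 0.72 or 1.03 SD. The half-width follows from the sample size, with all infants evaluable and approximate normality. The percentages rest on assumed effects, since no SD is given. The documents do not support any conclusion that the pilot itself is invalid or that its feasibility assessment is compromised.

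**What to change.** Reword the sizing sentence in Sample Size/Statistics along these lines:

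*The future RCT will be sized on a clinically important difference in 48-hour morphine equivalents, set by the investigators before the pilot results are analysed. The calculation will use the pilot SD on the scale that the RCT will analyse, with a stated allowance for its uncertainty (for example the upper one-sided 80% limit, SD × 1.14), and the pilot recruitment and consent rates. The observed effect and its 95% confidence interval will be reported to judge whether that difference is plausible, and will not set the sample size.*

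Bring the primary-aim hypothesis and the sentence on the expected trend into line. The investigators must supply the difference, because the documents give none. The 80% limit is one convention among several.

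For this pilot the cost is wording only, since the SDs and rates are already planned. With the example allowance the future RCT is about 30% larger than with the uncorrected SD (factor 1.297). Some risk remains if the true effect is smaller than the chosen difference, or if the outcome is skewed and the SD is taken on the raw scale.

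### The claim of adequate power at 15 per arm has no SD or target power behind it, and the 48-hour opioid total is compared without adjustment for weight, which may cost precision

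*Combined protocol and SAP*

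**What the plan says.** **Power.** The Sample Size/Statistics section of the combined protocol and SAP first says that "the proposed study is likely underpowered to detect a statistically significant result". It then cites a retrospective study of 17 patients that "examined the use of paravertebral nerve catheters in infants undergoing thoracotomy to repair long-gap esophageal atresia" and reported 36% less morphine per day (p<0.001). The section sets a condition, "If such a dramatic decrease in morphine consumption is observed during our prospective study", and on that condition claims enough power: "then it is adequately powered at current sample size 15 in each arm, total 30 patients". No SD, control mean, target power or calculation is given anywhere.

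**Outcome.** The Primary Aim asks "whether total narcotic administration is less in subjects who receive the peripheral nerve block". Its evaluation method reads: "All narcotics used in the 48-hour post-op period will be tabulated and converted to morphine equivalents". Nothing divides the total by body weight.

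**Population and analysis.** The Inclusion Criteria set a lower limit of 2.5 kg and an age below 12 months, with no upper weight. The Design section describes permuted blocks and no stratification. The analysis text plans a two-sample t-test or Wilcoxon rank-sum test, two-sided at 5%, with no covariate.

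**Use of the result.** The plan states that "the results (i.e. effect sizes) from this study will be used in sample size and power calculations for a future, larger RCT".

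**The concern.** Power depends on an assumed true effect and an SD. The plan supplies neither an SD nor a target, so 15 per arm cannot be reproduced from its contents, and the favourable sentence conflicts with the cautious one before it. The 36% is also a daily figure from catheters observed over several days, while this trial gives a single-shot block and counts 48 hours.

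The outcome definition bears on the missing SD. If larger infants receive more post-operative opioid, differences in weight add to the spread of the total, and nothing in the design or analysis removes them. The treatment effect would then be estimated less precisely than the same 30 infants allow, and that estimate is what the pilot is meant to pass to the next trial.

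**Working it through.** **Inputs from the plan:** 15 per arm; two-sided 5%; 36% fall; lower weight 2.5 kg.

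**Assumptions, because the plan is silent:** 80% target power; upper weight of 4, 5, 8 or 10 kg with uniform weights; per-kg CV of 40%; log-normal per-kg use; no dropout.

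**1. The plan's figure.** It cannot be reproduced without an SD and a target power, so I solved for the SD that would make it true.

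- Noncentral t, 28 df, critical value 2.048, noncentrality d × √(15/2). Power of 80% needs d = 1.060.
- Equal SDs: SD limit = 0.36 / 1.060 = 0.340 of the control mean.
- SD proportional to the mean: √((1 + 0.64²)/2) = 0.8395, so the limit is 0.340 / 0.8395 = 0.405.
- Power with equal SDs at SD/mean of 0.25, 0.30, 0.40 and 0.50 is 97%, 89%, 66% and 48%.

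The sentence is therefore true for some plausible SDs and false for others.

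**2. Observed versus true effect.** Significance needs an observed standardised difference of at least 2.048 × √(2/15) = 0.748. An observed 36% fall is significant if the observed SD is at most 0.36 / 0.748 = 0.481 of the control mean (equal SDs). That is a statement about the p-value, not about power.

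**3. Spread added by weight, if use is proportional to weight.** For weights uniform from 2.5 to U kg, CV of weight = [(U − 2.5)/√12] / [(U + 2.5)/2]. CV of total = √[(1 + CVw²)(1 + 0.40²) − 1]. Then d = 0.36 / (CV of total × 0.8395).

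| U (kg) | CV of weight | CV of total | Power, total (formula) |
|---|---|---|---|
| 4 | 0.133 | 0.425 | 76% |
| 5 | 0.192 | 0.451 | 71% |
| 8 | 0.302 | 0.516 | 59% |
| 10 | 0.346 | 0.547 | 55% |

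Without weight spread, d = 0.36 / (0.40 × 0.8395) = 1.072 and power is 81%.

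**4. Simulation of the analysis options** (true 36% proportional fall, 15 per arm; results may move by about a point between runs).

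| Analysis | Use proportional to weight, U = 4/5/8/10 | Use unrelated to weight, U = 4/5/8/10 |
|---|---|---|
| Total, unadjusted t-test | 79/74/62/56% | 84% throughout |
| Total per kg, t-test | about 84% throughout | 78/74/58/50% |
| Total, linear adjustment for weight | about 78–81% | about 82% |
| Log total on arm and log weight | about 85% | about 85% |

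Part of the advantage of the log-log model comes from simulating log-normal use, so it should not all be credited to weight. Linear adjustment carries no such advantage and still recovers most of the loss at the wider weight ranges.

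**The case against.** The strongest objection is that the plan does not say post-operative opioid use scales with weight. The only weight-based opioid dose in Study Description is fentanyl at induction, before the 48-hour post-operative window; the text on post-operative pain control gives no dose basis for fentanyl, morphine or oxycodone. This stands. The loss is conditional, and if nearly all infants weigh 2.5–4 kg it is small.

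A reader might infer that the outcome should simply be redefined per kg. The documents do not support that: if use is unrelated to weight, the last column above shows that division loses power. Covariate adjustment avoids this risk.

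A reader might also infer that the SD handed to the next trial would be wrong, or that a chance weight imbalance could pass for a treatment effect. Both go too far. The SD is correct for the total as measured, and under randomisation chance imbalance is already in the standard error and the 5% error rate.

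The cited p<0.001 in 17 patients might be taken to settle the variability. If it compared 8 with 9 patients, d would be at least 4.07 × √(1/8 + 1/9) = 1.98, so the CV would be at most 0.36 / 1.98 = 0.18 and power here above 99%. If it was a paired comparison, the upper limit on the CV would be about 0.26 to 0.48 for within-patient correlations of 0 to 0.7, with power at those limits from 95% down to 51%. The plan does not give that study's design or say whether its outcome was per kg, so the figure settles nothing.

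Finally, the plan makes feasibility primary, treats efficacy as exploratory and already requires SDs and effect sizes with 95% confidence intervals. That limits the severity. It does not supply the missing SD or make the two power statements agree.

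**Conclusion.** Two linked points hold.

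First, the claim of adequate power is unsupported and sits awkwardly beside the plan's own caution. It would be tempting to say that the claim is wrong or that the trial is underpowered. The documents do not show this, because the SD that would decide it is absent.

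Second, the opioid total is compared with no allowance for weight. If use is proportional to weight and the per-kg CV is 40%, power for a true 36% fall is about 79% with an upper weight of 4 kg and 56% with 10 kg, against roughly 80% with linear adjustment. If use does not depend on weight, nothing is lost under the present plan and adjustment costs about 2 points.

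The sizes rest on the assumed 80% target, uniform weights, upper weights, per-kg CV and proportionality. Severity is minor to moderate.

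**What to change.** 1. **Sample Size/Statistics, analysis text.** Prespecify that the morphine-equivalent comparison is adjusted for weight at surgery: for example, a linear model of log morphine equivalents on arm and log weight, or of the total on arm and weight if any infant has a zero total. Report the treatment effect with its 95% confidence interval, and the residual SD, stating its scale, for sizing the later trial. Use per kg may be reported descriptively.

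2. **Sample Size/Statistics, power sentence.** Delete it, or replace it with:

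> With 15 per arm, a two-sided 5% t-test has 80% power (an assumed target) for a true standardised difference of 1.06. A true 36% reduction meets this only if the SD is at most about 34% of the control mean with equal SDs, or about 40% if the SD is proportional to the mean.

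**Cost.** Two short text changes, no extra patients and no new data, since weight at surgery is already needed for eligibility. The adjustment uses one degree of freedom and about 2 points of power if weight does not matter. A log model reports a ratio rather than a difference in means, so the difference that the plan already requires should be kept beside it.
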